### II. Methods

- Patients will be randomized to one of two treatment groups: temporary external fixation or temporary splinting. Both temporary treatments are those routinely used/available at the UCD health system. Subjects are to wear the temporary treatment method until definitive surgery.
- Safety endpoints occur at conclusion of the definitive fixation of their calcaneal fracture.

## PROTOCOL TITLE: Staged External Fixation of Acute Calcaneal Fractures

- All subjects will receive standard perioperative and operative treatment of their injury. Patients will receive standard clinical follow up for which their healing and functional status will be continually evaluated.
- Follow up after surgery will be at 6 time points: 2 weeks, 6 weeks, 12 weeks, 6 months, 1 year, 2 years
- The research related activities are randomization, using SOS surveys at specified time points, and collecting/reporting data regarding the outcomes from routine visits and survey responses.

### **III. Outcomes**

#### **Primary outcome**

1. Time to definitive surgery
2. Soft tissue complications (at routine follow ups which are 2, 6, & 12 weeks, and 6, 12, & 24 months after surgery)

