**2) Objectives**

Aim:

- Determine if external fixation decreases soft tissue complications compared to splinting.
- Determine if external fixation decreases time to definitive surgical stabilization and improves final fixation compared to splinting.
- Determine if external fixation improves functional outcomes as evaluated by validated functional scoring systems.

Hypothesis:

- External fixation improves definitive fixation and functional outcomes of acute calcaneal fractures with decreased complication rates compared to splinting

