#### **4) Inclusion and Exclusion Criteria**

Inclusion Criteria	Exclusion Criteria

• Voluntary consent

• Age 18 to 69

• Clinical and/or advanced imaging confirming an acute calcaneal fracture that has occurred within 2 days of which, eventually definitive surgery is recommended/accepted.

	

• unable to consent

• age <18

• Prior surgery of the affected extremity

• Prisoners

• Pregnant women

• Inflammatory arthritis

• Non-english speaking spatients

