## 5) Study Timelines

- Study will begin after IRB approval
- Patient recruitment will take place over two years, however this may be longer depending on the number of patients who require definitive surgery
- The duration of the subject's participation in the study will conclude at two year postoperatively
- The primary analysis will be complete within 3 years of the study start time

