## 6) Study Endpoints and Procedures involved

### I. Design

- Subjects will be recruited from the UC Davis Medical Center. Adults diagnosed with an acute (<1-2 days from injury) calcaneal fracture recommended for operative treatment will be offered enrollment into the study.
- A total of 100 patients will be enrolled in the study. The sample size can be calculated at 35 per treatment groups after considering multiple comparisons and using an 80% power and an  $\alpha = 0.05$ . This would require a minimum of 70 patients for the study; however, factoring in a 30% dropout rate, a minimum of 100 patients will be enrolled into the study with a minimum of 50 patients per group.

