#### **Secondary outcomes**

1. Union rate via standard weight bearing plain radiographs ( harris axial/lateral views) at 6 weeks, 12 weeks, 6 months, 1 year, and 2 years after surgery. We will also obtain a 1X CT scan of the injured foot at 1 year after surgery to monitor for arthritic progression.
2. Radiographic parameters(Bohler's angle, clancaneal height/width/length, and angle of Gissan)
3. Other complications
4. Clinical outcomes will be evaluated to monitor patients' activity levels, pain, and functional status. This will be done primarily using the web-based Surgical Outcome System™ (SOS)
  - The SOS is currently a UCD IRB approved study (IRB # 1192222). It is a large international web-based registry that permits collection of baseline characteristics of patients undergoing orthopedic procedures. The data is collected using direct entry into a web-based collection system called the Surgical Outcome System (SOS). By completing these surveys, the investigator surgeon has the opportunity to monitor the subjects progress after treatment, even when they are not scheduled to see the provider. The investigator surgeon will also be able compare the outcomes to the average de-identified global data.
  - In order to utilize the web-based surveys, we would invite patients to dual enroll and consent into SOS. If, the subject forgoes SOS participation, the surveys may be filled out manually and this data will not be part of SOS.
  - Subjects fill out surveys before visits at 7 total time points: preoperatively, & postoperatively at 2, 6, and 12 weeks and 6 months, 1 and 2

**PROTOCOL TITLE:** Staged External Fixation of Acute Calcaneal Fractures

years. The surveys may include the Visual Analogue pain score(VAS), Patient-reported outcomes measurement information system 10 short form (PROMIS 10), or Veterans RAND 12 item Health survey (VR-12), Foot function index questionnaire (FFI-R) or Foot and Ankle Ability measure activities of daily living (FAAM ADL), and FAAM sport

**IV. Analysis:** The data will be analyzed for differences between splinting and external fixator treatment groups. Data will be stratified and analyzed for further differences in outcomes based on other factors (ie: demographics, comorbidities..)

- To assess significance the alpha level will be set at <0.05.
- Continuous data will be reported as means, standard deviation(SD), range, with 95% confidence intervals

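### Primary outcome 1, time to definitive surgery, has no time origin and no rule for a randomised patient who has no definitive surgery; arm-related bias is possible, not shown.

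*Combined protocol and SAP*

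**What the plan says.** Section 6, III. Outcomes lists primary outcome 1 as "Time to definitive surgery" and adds nothing to it. The matching aim in Section 2 is "Determine if external fixation decreases time to definitive surgical stabilization and improves final fixation compared to splinting", which gives no origin either.

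Three candidate origins can be found in the text:

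- **Injury.** Section 4 admits an "acute calcaneal fracture that has occurred within 2 days of which, eventually definitive surgery is recommended/accepted", so injury can precede entry by up to 2 days. Section 6, I. Design gives a similar window.
- **Randomisation.** Section 6, II. Methods assigns patients to external fixation or splinting.
- **Application of the temporary treatment.** The same section states: "Subjects are to wear the temporary treatment method until definitive surgery". It does not say when either treatment is put on.

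For analysis, Section 6, IV states: "Continuous data will be reported as means, standard deviation(SD), range, with 95% confidence intervals". No time-to-event method, censoring rule or competing-event rule appears anywhere.

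On whether everyone reaches surgery, the text points both ways. II. Methods presumes that all subjects receive operative treatment. Section 4 asks only that surgery be recommended or accepted at some later point. Section 10 allows voluntary withdrawal at any time, and withdrawal by the researchers if health changes or requirements are no longer met. I. Design allows for 30% dropout without splitting it by reason or stage. All follow-up visits are counted from surgery.

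**The concern.** Two decisions about a primary outcome are left open: when the clock starts, and what happens to a randomised patient with no surgery date. Section 15 notes that the treatments are visible to the subjects, so the trial is not blinded to them, and choices of this kind are best fixed before data are seen.

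The second gap matters more. A mean of observed times is a mean among the operated. Section 3 explains that the delay exists so that swelling can subside, so soft tissue recovery is part of what this outcome measures. If a patient goes unoperated because recovery is poor, the mean omits an unfavourable result. If that happens more in one arm, the comparison is no longer between the groups as randomised.

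The first gap matters only for some choices of origin. Injury or randomisation, used alike in both arms, would serve. An origin at application would bring in any difference between arms in how long application takes.

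**Working it through.** **1. The plan's own figures.** Dropout step: 70 / (1 − 0.30) = 100, or 50 per arm, which reproduces the stated enrolment. The 35 per group cannot be reproduced, because no effect size, SD or event rate is given. Solving backwards for a comparison of means at 80% power and two-sided 0.05 (sidedness is not stated, so this is an assumption):

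d = √(2/35) × (1.960 + 0.842) = 0.67 SD.

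At two-sided 0.025, to allow for two primary outcomes, d = 0.74 SD. These serve only as a yardstick for the sizes below.

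**2. Effect of patients without a surgery date.** The documents give no times, so all inputs here are assumptions: lognormal times with mean m and SD of 10/4, 14/6 or 14/8 days, and 5% or 10% of one arm lost (2.5 or 5 of 50 patients). With σ² = ln(1 + (SD/m)²):

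- *Slowest fraction k lost:* remaining mean = m × Φ(z₁₋ₖ − σ) / (1 − k).
- *Fraction k lost at random from the slowest 30%:* remaining mean = (m − k × T) / (1 − k), where T = m × [1 − Φ(z₀.₇ − σ)] / 0.30.

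Example, 14/8 days and the slowest 10% lost: σ = 0.532; Φ(1.282 − 0.532) = 0.773; 14 × 0.773 / 0.90 = 12.03. The fall is 1.97 days.

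| Mean/SD (days) | Slowest 5% lost | Slowest 10% lost | 5% from slowest 30% | 10% from slowest 30% |
|---|---|---|---|---|
| 10/4 | 0.57 | 0.95 | 0.25 | 0.54 |
| 14/6 | 0.86 | 1.43 | 0.38 | 0.80 |
| 14/8 | 1.22 | 1.97 | 0.50 | 1.05 |

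The entries are the fall in that arm's mean, in days. The range is 0.25 to 1.97 days, or about 0.06 SD (0.50/8) to 0.25 SD (1.97/8). Against the 0.67 SD yardstick, that is roughly 9% to 37% of the detectable difference.

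**3. Cases with no bias.** If losses are unrelated to healing speed, the expected mean of the remaining patients is m and the shift is zero. If both arms have the same distribution of times and lose the same fraction in the same way, both means fall equally and the difference is unchanged. The table therefore describes one-sided, selective loss only.

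**4. Effect of the origin.** Let w be the wait from randomisation to application. With an origin at application, observed difference = difference from randomisation − (w in the fixator arm − w in the splint arm), where each difference is fixator minus splint. An origin at injury adds an interval that precedes allocation, and randomisation balances it in expectation. Only the application origin can carry an arm-related shift, and only if w differs.

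If the clock did start 1 day later in one arm, with no true effect and 35 per group, the chance of a significant result favouring that arm is Φ(1 / (SD × √(2/35)) − 1.96). This is 29%, 13% or 9% for an assumed SD of 3, 5 or 7 days, against a nominal 2.5%.

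**The case against.** The strongest reply is that the plan expects everyone to be operated on. Operative treatment is an entry condition in Sections 4 and 6, and II. Methods says all subjects receive it. An unoperated patient is then an unplanned contingency of unknown size. This stands as a limit on size, but it does not remove the need for a rule, because Section 10 permits withdrawal before surgery and the 30% dropout is not confined to later stages.

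A reader might take Section 5, "Patient recruitment will take place over two years, however this may be longer depending on the number of patients who require definitive surgery", as saying that some enrolled patients will not need surgery. That sentence is about how long recruitment lasts. Its natural reading is the supply of eligible patients, and it is not evidence of attrition after entry.

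A reader might also infer that the hardest cases drop out of the means. The documents do not say who would go unoperated; a patient who simply declines surgery need not be a slow healer.

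Nor do the documents show that the fixator arm gains from a later clock start. That needs an origin at application and a longer wait for fixators than for splints, and neither is stated.

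Finally, Section 6, IV describes how data are reported. That a patient without a date is left out is inferred from the absence of any other rule. The inference is sound, since a mean needs a value, but it is not a stated exclusion.

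**Conclusion.** The gap is real: a primary outcome has no origin, and a randomised patient without definitive surgery has no place in its only stated summary. The missing origin alone is close to missing detail, since two of the three candidates would treat the arms alike. The more substantial point is the method, because a time-to-event outcome is summarised only by a mean that omits patients without the event.

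The direction and size of any bias depend on who is not operated on and in which arm, and the documents do not settle either. Bias is near zero if losses are unrelated to healing or balanced. With 5 to 10% of one arm lost, all from its slower patients, that arm's mean falls by about 0.25 to 2.0 days. This rests on assumed lognormal times with means of 10 to 14 days and SDs of 4 to 8 days. The plan should be changed on this point, but the text does not support a claim that either arm is favoured. Confidence is medium.

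**What to change.** - **Definition.** State primary outcome 1 as days from randomisation to the start of definitive surgery, in both arms. Record the date and time of injury so that days from injury can be reported alongside.
- **Analysis.** Include all randomised patients by assigned arm. Compare the cumulative proportion operated on over time, with curves and median by arm and one named test (for example log-rank or Gray), up to a prespecified cut-off. This replaces means among the operated.
- **Patients without surgery.** Censor those who withdraw before surgery at last contact. Count a final decision against surgery as a competing event, that is, as not having reached surgery. Report both by arm with reasons.

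The cost is a few sentences in the outcome and analysis sections; enrolment, alpha and treatment are unchanged. Randomisation and injury times must be captured, because the documents do not say that they are. Since visits are counted from surgery, the status of unoperated patients at the cut-off also needs to be collected. The main result becomes a curve or median, not a mean.

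### Primary outcome 2 schedules soft tissue complications only at visits after definitive surgery, so events that arise and resolve under the fixator or splint are not assured of being counted

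*Combined protocol and SAP*

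**What the plan says.** Section 6.III lists two primary outcomes. The first is "Time to definitive surgery". The second is "Soft tissue complications (at routine follow ups which are 2, 6, & 12 weeks, and 6, 12, & 24 months after surgery".

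Section 6.II sets the period of differing treatment: "Subjects are to wear the temporary treatment method until definitive surgery". The same section gives the visit schedule, "Follow up after surgery will be at 6 time points: 2 weeks, 6 weeks, 12 weeks, 6 months, 1 year, 2 years", and describes the research activity as including "collecting/reporting data regarding the outcomes from routine visits and survey responses". Under section 5, participation "will conclude at two year postoperatively".

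The first aim in section 2 asks whether external fixation reduces soft tissue complications relative to splinting, with no restriction to the time after surgery.

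Three other places bear on complications. Section 6.II says "Safety endpoints occur at conclusion of the definitive fixation of their calcaneal fracture", without saying what those endpoints are. Section 6.III has a secondary outcome, "Other complications", with no assessment times. Section 9 has the principal investigator track complications as part of usual care.

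**The concern.** The assigned methods differ only between randomisation and definitive surgery, and section 3 expects that interval to last until swelling subsides. Skin problems under a splint, or pin-site problems with a fixator, would arise then. The outcome meant to compare soft tissue complications is first assessed 2 weeks after that interval ends.

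The uncounted interval may also differ by arm. The protocol hypothesises that the fixator shortens the time to surgery and makes that time its other primary outcome. If so, the complication schedule starts at a point that treatment itself moves.

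At stake is how complete the comparison is. Events caused by the temporary method could be left out, or counted for some patients and not for others, depending on who reads the chart.

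**Working it through.** **Can another provision bring a resolved pre-operative event into primary outcome 2?**

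- *Safety-endpoint sentence (6.II):* one time point at the end of definitive fixation, content undefined, no link to the primary outcome.
- *Secondary outcome on other complications (6.III):* untimed, and most naturally read as complications other than soft tissue ones.
- *Investigator tracking (section 9):* may record the event, but does not assign it to an outcome.
- *Pre-operative survey (6.III):* the named instruments cover pain, function and general health; none is described as recording soft tissue complications.
- *The 2-week visit:* might pick the event up from the history, but the protocol does not require this.

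So recording is possible, but counting is neither assured nor required to be alike in the two arms.

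**The plan's own figures.** Section 6.I gives 35 per group, a minimum of 70, and 30% dropout. 70 / (1 − 0.30) = 100 and 35 / (1 − 0.30) = 50, which match the stated totals. The 35 cannot be reproduced, because no effect size or event rate is given. Both group sizes are used below for scale.

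**Illustration. Every rate is an assumption.** Post-operative rates: fixator 10%, splint 20%. Benefit = splint − fixator. If no pre-operative event is captured, the scheduled outcome shows 20 − 10 = 10 points.

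Full count under independence: total = 1 − (1 − pre)(1 − post).

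| Case | Pre-op, fixator / splint | Fixator total | Splint total | Full-count benefit | Gap from 10 |
|---|---|---|---|---|---|
| 1 | 15% / 5% | 1 − 0.85 × 0.90 = 23.5% | 1 − 0.95 × 0.80 = 24.0% | 0.5 | 9.5 (benefit overstated) |
| 2 | 5% / 10% | 1 − 0.95 × 0.90 = 14.5% | 1 − 0.90 × 0.80 = 28.0% | 13.5 | 3.5 (understated) |
| 3 | 10% / 10% | 1 − 0.90 × 0.90 = 19.0% | 1 − 0.90 × 0.80 = 28.0% | 9.0 | 1.0 (overstated) |

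*Overlap free to differ by arm.* Each arm's total lies between max(pre, post) and pre + post.

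- Case 1: fixator 15 to 25%, splint 20 to 25%. Benefit from 20 − 25 = −5 to 25 − 15 = +10.
- Case 2: fixator 10 to 15%, splint 20 to 30%. Benefit +5 to +20.
- Case 3: fixator 10 to 20%, splint 20 to 30%. Benefit 0 to +20.

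The largest gap is in case 1: 10 − (−5) = 15 points.

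*Half of the pre-operative events captured, equally in both arms, under independence.* Scheduled rate = 1 − (1 − 0.5 × pre)(1 − post).

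- Case 1: 16.75% vs 22.00%, benefit 5.25, gap 4.75.
- Case 2: 12.25% vs 24.00%, benefit 11.75, gap 1.75.
- Case 3: 14.50% vs 24.00%, benefit 9.50, gap 0.50.

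*Capture in one arm only, case 3.* If only fixator events are picked up: 20.0 − 19.0 = 1.0 point against a full count of 9.0. If only splint events are: 28.0 − 10.0 = 18.0 points. Unequal capture can matter even when the pre-operative rates are equal.

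**Sampling error for scale.** The 95% half-width for 10% vs 20% is 1.96 × √(0.10 × 0.90/n + 0.20 × 0.80/n) = 1.96 × √(0.25/n). With n = 50 this is 13.9 points; with n = 35 it is 16.6 points.

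**The case against.** The strongest reply is that section 6.III states when complications are assessed, not when they must have begun. A 2-week review that takes the interval history would comply. With investigator tracking in section 9 and a pre-operative survey time point, pre-operative events could well reach the data. This stands as far as it goes: a reader might infer that such events are excluded or never recorded, and the documents do not say that. But a permitted route is not a required one, and the wording does not settle whether a resolved event counts.

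Second, a post-operative outcome is a defensible choice. Section 3 presents the temporary fixator as a way to reduce soft tissue complications of open fixation. That also stands, so the outcome is incomplete for the stated aim rather than invalid. A pre-operative problem that delays surgery may also show indirectly in the other primary outcome.

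Third, patients who never have surgery might be thought a large uncounted group. The documents do not support this. Section 4 enrols only patients for whom surgery is recommended and accepted. The 30% in section 6.I is general dropout, and section 10 covers general withdrawal. This is a side issue, although no rule says whether such patients' earlier complications count.

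Finally, every rate above is assumed, and with groups this small one might dismiss the gap as within sampling error. That is true of the independence cases, where the largest gap is 9.5 points. It is not true of the 15-point bound, which exceeds the 13.9-point half-width at 50 per arm. Nor does that comparison make a systematic omission harmless, since enrolling more patients would not remove it.

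**Conclusion.** The point holds as a gap in the outcome definition. Primary outcome 2 is scheduled only after surgery, although the methods differ only before it and the aim is not confined to the later period. No provision brings a complication that resolves under the fixator or splint into the outcome, or makes its handling the same in both arms.

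On the assumed rates, with no pre-operative capture and independence, the scheduled and full-count differences are 1.0 to 9.5 points apart. Equal half capture halves this to 0.5 to 4.75. Overlap that differs by arm can raise it to 15 points.

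A reader might infer that the plan favours the fixator. The documents do not support that: they give no complication rates, the assumed cases move in both directions, and neither the direction nor the size of any bias is established. The change is worth making because it completes the comparison cheaply, not because an error of known size has been shown.

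**What to change.** Count soft tissue complications from randomisation in all randomised patients. Up to surgery, abstract onset date and event type from the routine record; afterwards, use the six existing visits. Apply the same abstraction rule in both arms.

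Report by arm:

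- the pre-operative component, with pin-site and splint-related skin events shown separately;
- the post-operative component;
- the total.

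Name in advance which of these is the primary comparison. If it stays post-operative, say so and report the other two beside it. For the few patients who never have surgery, count from randomisation using whatever routine records exist. State how the safety-endpoint sentence in section 6.II and the secondary complications outcome relate to this count.

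The cost is some chart abstraction and a list of qualifying event types, since the protocol does not define the term. No new visit is needed for patients who have surgery; records for those who do not may be incomplete. The total mixes events of different weight and includes pin-site events possible in only one arm, hence the separate components. The fixator rate may look less favourable.
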